#### **9.1.1.3 Extent of Exposure Based on the Subject's e-Diary Registration**

When deriving extent of exposure based on the e-Diary, days with Voiding Diary assessments as well as days without Voiding Diary assessments will be considered.

For each visit with an e-Diary assessment of IMP intake, the duration of exposure in days is derived as 1 + the difference between the date of the latest intake of IMP after the previous visit and the date of the earliest intake of IMP after the previous visit, and the extent of exposure in number of doses will be derived as the number of days where the subject answered Yes to "*Did you take your study medication [during this diary day]?*". In case two or more visits with an e-Diary assessment of IMP intake fall into the same visit window, the duration will be derived as the difference between the latest date of intake of IMP in any of the diaries and the earliest date of intake of IMP in any of the diaries, and the number of doses will be derived as the sum of doses across the diaries.

Duration and number of doses at Visit 3 will be summarized overall and by sex for the ITT-ENR analysis set and for the Safety-ENR analysis set.

Duration and number of doses will be summarized by treatment group and visit, overall and by sex, for the ITT-RT analysis set and for the Safety-RT analysis set.

#### **9.1.1.4 Agreement of the Two Sources**

For each visit with e-Diary assessments of the exposure (scheduled Visits 3, 5, 6, 7, and 8), the number of doses according to the e-Diary in Section 9.1.1.3 will be subtracted from the investigator-assessed number of doses of bottles and ODT, respectively, derived for the same period according to Section 9.1.1.2. The differences will be summarized by treatment group, sex, and visit; Visit 3 will be summarized for the ITT-ENR analysis set and for the Safety-ENR analysis set; the post-randomization visits will be summarized for the ITT-RT analysis set and for the Safety-RT analysis set.

### 9.1.2 Treatment Compliance

Compliance will be derived separately for each of the three exposure measures of number of doses: the number of bottles and the number of ODT (Section 9.1.1.2), and the number of doses according to the e-Diary (Section 9.1.1.3). For each exposure measure of number of doses, compliance in % during a specific period (that is, a period between two visits, the active run-in period, the randomized-treatment period, or total exposure duration) will be derived as the exposure measure of number of doses for the period divided by the corresponding exposure duration in days for the same period calculated in Section 9.1.1.2 as the end date minus the start date of the period, and multiplied by 100 to obtain a percentage.

Compliance during the active run-in period will be summarized as overall and by sex for the ITT-ENR analysis set and for the Safety-ENR analysis set.

Compliance will be summarized by treatment group and visit, overall and by sex, for the ITT-RT analysis set and for the Safety-RT analysis set.

In addition, for each visit with Voiding Diary assessments, treatment compliance will be derived for the nights where the number of nocturnal voids can be derived. The treatment compliance in % during Voiding Diary assessment will be derived as the number of nights where the number of nocturnal voids can be derived and the subject answered Yes to “*Did you take your study medication during this diary day?*” divided by the total number of nights where the number of nocturnal voids can be derived in the Voiding Diary for the visit, and multiplied by 100 to obtain a percentage. Treatment compliance during Voiding Diary assessment will be summarized as a categorical variable by treatment group and visit for the ITT-RT analysis set and for the PP analysis data set.

## 10 Efficacy

### 10.1 General Considerations

For endpoints obtained from the Voiding Diary prior to a visit, the average of the endpoint across the 3 days will be interpreted as the cross-sectional observation of the endpoint in question at the specific visit, with the exception of the two endpoints, “Percentage of nights during the treatment period with at most one nocturnal void” and “Percentage of nights during the treatment period with complete response, i.e., with no nocturnal voids”.

If the baseline number of nocturnal voids is missing for a reason that can be considered to be missing completely at random (e.g., missing due to technical problems of the eDiary), the subject will not be included in any analyses that involve baseline measurements of nocturnal voids or other variables derived using baseline measurements of nocturnal voids.

The Bayesian dose-response analyses are conducted on aggregated averages, that is, outcomes averaged across preceding post-randomization visits. The posterior mean, median, and 95% credibility interval (2.5 and 97.5 percentiles of the posterior distribution) of quantities of interest as well as posterior probabilities of interest will be reported.

Frequentist inferences will rely on the appropriate choice of model and report p-values corresponding to the statistical test of the hypothesis of “no difference / no association” against the alternative of “any difference / any (linear) association”. The level of significance is set at 5% (two-sided).

Treatment comparison refers to the pair-wise comparison between each of the different doses of active treatment with FE 201836 and placebo. There are no planned adjustments for multiplicity when pair-wise testing the active treatment with different doses of FE 201836 versus placebo. Desmopressin is included as a benchmark treatment only. None of the primary, secondary or explorative analyses will include data from subjects treated with desmopressin. Explorative benchmarking analyses are further described in Section 10.5.

### 10.2 Primary Efficacy Endpoint

#### 10.2.1 Primary Analysis

The primary endpoint is the aggregated average of change from baseline-RT in number of nocturnal voids after 12 weeks of treatment, that is, averaged across all post-randomization visits. The objectives of the primary analysis are to establish Proof-of-Concept of FE 201836 and to estimate the dose-response profile of FE 201836. The analyses will be performed on the ITT-RT analysis set.

The overall trial outcome is proof-of-concept evaluated by the posterior probability that 500 µg FE 201836 has superior efficacy as compared to placebo ( $Pr(\mu_{500} < \mu_{Plb}) > 97.5\%$ ) based on a Bayesian analysis of the dose-response profile at Week 12 for the ITT-RT analysis set not including the active comparator desmopressin.

The dose-response profile will be characterized by the posterior estimates of the mean dose-response at each dose,  $\mu_d$ , corresponding to two nocturnal voids at baseline and the mean dose-response contrast versus placebo,  $\Delta_d$ , with their associated 95% credibility intervals. The posterior probabilities  $Pr(\Delta_d < -0.3)$ ,  $Pr(\text{dose } d \text{ is MED})$ , and  $Pr(\text{dose } d \text{ is ED}_{85})$ , will be tabulated. The dose-response curve relative to placebo will also be presented graphically with its 95% credible interval in the plots illustrating the therapeutic window (Section 10.4). No multiplicity adjustment will be performed.

The dose-response profiles are determined using the following model: Let  $x_{t,i}$  denote the observed cross-sectional change from baseline-RT in nocturnal voids (averaged across the nights in the Voiding diary corresponding to the visit) and let  $y_{t,i}$  denote the aggregated average change from baseline for subject  $i$ , averaged across post-randomization visits up to time  $t$  (for visit windows see Section 3.1.5):

$$y_{t,i} = \frac{\sum_{k=1}^t x_{k,i}}{t}, \quad t = 1, 2, 3, 4,$$

where  $t$  denotes the nominal post-randomization time points reflecting Visits 5, 6, 7 and 8, corresponding to Weeks 1, 4, 8, and 12, respectively. The final endpoint,  $y_{4,i}$  is modelled as being an observation of

$$Y_{4,i} \sim N(\beta \cdot (x_{0,i} - 2) + \mu_d, \sigma^2), \quad (1)$$

where  $x_{0,i}$  is the baseline-RT number of nocturnal voids,  $\sigma^2$  is the error variance, and  $\mu_d$  describes the dose-response relationship.  $\mu_d$  is assumed to follow a four-parameter sigmoidal model:

$$\mu_d = \alpha_1 + \frac{(\alpha_2 - \alpha_1)d^{\alpha_4}}{d^{\alpha_4} + \alpha_3^{\alpha_4}}, \quad (2)$$

where  $d$  is the dose measured in 100  $\mu\text{g}$  (so  $d=0, 0.5, 1, 1.5, 2.5, 3.5$ , or  $5$ ), and the interpretation of the parameters are:  $\alpha_1$  is the placebo response for a subject with 2 nocturnal voids at baseline;  $\alpha_2$  is the maximum response for a subject with 2 nocturnal voids at baseline;  $\alpha_3$  is the dose ( $ED_{50}$ ) at which 50% of the maximum effect is obtained; and  $\alpha_4$  is the slope parameter. In the primary analysis of  $y_{4,i}$ , the model parameters  $\theta = (\beta, \alpha_1, \alpha_2, \alpha_3, \alpha_4, \sigma^2)$  are modelled with the prior distributions  $\beta \sim N(0, 10^2)$ ;  $\alpha_1 \sim N(-1, 3^2)$ ;  $\alpha_2 \sim N(-0.5, 2^2)$ ;  $\alpha_3 \sim N^+(2, 2^2)$ ;  $\alpha_4 \sim N^+(5, 3.5^2)$ ; and  $\sigma^2 \sim IG(0.5, 0.605)$ , where the notation  $N^+(\eta, \zeta^2)$  refers to a positive truncated normal distribution, and the  $IG(a, b)$  is the inverse gamma distribution.

Missing data due to drop out or insufficient Voiding Diary data at Visit 8 will be imputed using a longitudinal model applied to the observed data including all visits, corresponding to a missing-at-random assumption. The longitudinal model of  $y_{t,i}$  is modelled conditional on an individual parameter,  $\delta_i$ , modelling  $y_{t,i}$  as

$$y_{t,i} = e^{\xi_t} (\beta(x_{0,i} - 2) + \mu_d + \delta_i) + \varepsilon_{t,i} \quad (3)$$

where  $\xi_4=0$ . Bayesian analysis will be based on the same priors as in the primary analysis described above for the  $\beta$  and the  $\alpha$  parameters, while the remaining parameters are modelled with the priors:  $\xi_t \sim N(0, 1)$ ;  $\delta_i \sim N(0, \tau^2)$  with  $\tau^2 \sim IG(0.5, 0.36125)$ , and  $\varepsilon_{t,i} \sim N(0, \lambda_t^2)$  with  $\lambda_t^2 \sim IG(0.5, 0.125)$ .

A total of 1000 imputations of the missing  $y_{4,i}$  will be performed. In the multiple imputation of the missing  $y_{4,i}$  for the primary analysis, a sample of size 1000 of the model parameters,  $\pi = (\xi_1, \xi_2, \xi_3, \beta, \alpha_1, \alpha_2, \alpha_3, \alpha_4, \delta_i \ (i=1, \dots, 300), \lambda_1^2, \lambda_2^2, \lambda_3^2, \lambda_4^2)$ , is first sampled from the posterior for the Bayesian analysis of the longitudinal model, using the seed=2720, a burn-in of 10 000 and a thinning factor of 50. Then for each set of model parameters,  $\pi_s$ , the imputed value of a missing  $y_{4,i}$  is obtained by adding a normally distributed error,  $\varepsilon_{4,i,s}$ , with seed=152 to the conditional mean of  $y_{4,i}$  (conditional on  $\delta_{i,s}$ ), giving a single imputation,  $y_{4,i,s}$ , thereby capturing all the variability in each imputed  $y_{4,i,s}$ .

For each of the imputed data sets, the Bayesian analysis of the (possibly imputed)  $y_{4,i}$  will be performed with a seed=10000+s using a burn-in of 10 000, and a single set of the model parameters  $\theta_s$  is obtained as number 50+s after the burn-in of the generated posterior values of  $\theta$ . The set  $\{\theta_s; s=1, \dots, 1000\}$  will be used to derive the  $\mu_d$  and  $\Delta_d$  with 95% credibility intervals and the posterior probabilities,  $Pr(\Delta_d < -0.3)$ ,  $Pr(\text{dose } d \text{ is MED})$ , and  $Pr(\text{dose } d \text{ is ED}_{85})$ .

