where $Y_{t,i}$ is the change from baseline in number of nocturnal voids at visit t for subject i , d is the dose, $e^{\gamma t}$ the fraction of the effect at Visit t (Week 1, Week 4 or Week 8) as compared to the Month 3 visit ($\gamma_t=0$ at Month 3), δ_i the random subject effect and ε_t the independent $N(0, \lambda_t^2)$ distributed error term. The dose-response for subject i , $\mu_{d,i}$, is adjusted for the number of baseline voids ($x_{0,i}$) and modelled using the sigmoidal E-max model, i.e.,

$$\mu_{d,i} = \beta x_{0,i} + \alpha_1 + \frac{(\alpha_2 - \alpha_1) d^{\alpha_4}}{d^{\alpha_4} + \alpha_3^{\alpha_4}} = \beta x_{0,i} + \mu_d$$

Inference will be based on a Bayesian analysis using sufficiently non-informative priors on respective parameters. The trial will be considered successful if the maximum dose has a greater than 97.5% posterior probability of being better than placebo, i.e., if $\Pr(\mu_{\text{MAX}} < \mu_{\text{Plb}}) > 97.5\%$.

Response-adaptive Decision Rules

The double-blind treatment period is based on a response-adaptive Bayesian top-down design. After an initial 125 subjects have been randomised to placebo, 500 µg FE 201836 (the highest dose) or desmopressin in a 2:2:1 ratio an interim analysis will take place to stop for futility if the $\Pr(\mu_{\text{MAX}} - \mu_{\text{Plb}} < -0.3) < 10\%$, where $\Pr(\cdot)$ denotes posterior probability (under the assumed monotonic dose-response relation, i.e. smaller doses will be less effective).

If not stopped for futility, all treatment arms will be opened up for randomisation, subjects can be randomised to placebo, desmopressin or to any FE 201836 dose (50-500 µg) in a 2:1:7 ratio. When allocated to a FE 201836 dose (7/10), unrestricted randomisation will be used to allocate a subject

to a specific FE 201836 dose using an allocation probability that is the average of $I(\text{dose is MED})$ and $I(\text{dose is ED}_{85})$, where $I(\text{target})$ is the probability that “dose is target” scaled by the squared standard error at that dose. The MED is the lowest dose that has at least a $\Delta=0.3$ larger reduction in mean nocturnal voids as compared to placebo and the ED_{85} is the lowest dose that achieves at least 85% of the effect of the maximum dose (500 μg).

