3.1.2 Overall Design and Control Methods

This is a randomised, double-blind, placebo-controlled, response-adaptive, dose-finding trial investigating the efficacy, safety and tolerability of 6 different oral doses (50-500 µg) of FE 201836, with desmopressin as a benchmark, during 12 weeks of treatment for nocturia due to NP in adults.

The trial will comprise 8 visits (Section 3.1.1) to the clinic and will consist of a 2-week screening/lifestyle changes period where no IMP will be given, an enrichment period consisting of a 1-week single-blind (to subjects) active run-in period and a 1-week washout period, and a 12-week double-blind randomised treatment period for each subject (Figure 3-1). During the active run-in period the trial subjects will receive 500 µg FE 201836 and placebo to assess safety and establish that subjects who respond to treatment with FE 201836 are included in the trial (i.e., an enrichment design).

The 12-week double-blind randomised treatment period of the trial will follow a response-adaptive Bayesian top-down design. Initially subjects will be randomised to: placebo, 500 µg FE 201836 or desmopressin (for benchmarking only). When approximately 125 subjects have been randomised to the trial, an interim analysis will be conducted to investigate the efficacy of 500 µg FE 201836. If 500 µg FE 201836 is not sufficiently efficacious compared to placebo the trial will be stopped for futility. If 500 µg FE 201836 is efficacious additional doses of FE 201836 (doses 50-350 µg) will be opened up for randomisation of new subjects in order to identify the Minimum Effective Dose (MED) and near maximal Effective Dose (ED₈₅). The ED₈₅ is the lowest dose that achieves at least 85% of the effect of the maximum dose (500 µg). After the first interim analysis, subsequent interim analyses will take place every 8 weeks to reassess the randomisation allocation probabilities to 50-500 µg FE 201836, based on observed responses at the respective interim locks. For more information regarding the interim analyses, please refer to Section 3.3 and Section 9.11.2.

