4.1.1 Inclusion Criteria

Each subject must meet the following inclusion criteria between Visit 1 (screening) through Visit 4 (randomisation):

1. Written informed consent prior to performance of any trial-related activity
2. Adults ≥ 18 years of age (at the time of written consent)
3. Female subjects of child-bearing potential must be willing and able to use adequate contraception throughout the trial. Documentation of an acceptable effective method of contraception must be available. All pre- and perimenopausal subjects have to perform pregnancy tests. Amenorrhea of more than 12 months duration based on the reported date of the last menstrual period is sufficient documentation of post-menopausal status and does not require a pregnancy test
4. Medical history of, or subject reported nocturia symptoms during the 6 months prior to Visit 1
5. ≥ 2 nocturnal voids (an average over 3 days) as documented in the 3-day e-Diary prior to Visit 2
6. The largest single voided volume must be ≥ 200 mL (at least 1 void ≥ 200 mL) as documented in the 3-day e-Diary prior to Visit 2
7. Nocturnal polyuria, defined as $NP_i > 33\%$, a ratio of NUV in excess of 33% of total daily (24-hour) urine volume as documented in the 3-day e-Diary prior to Visit 2
8. ^b
9. $\geq 20\%$ decrease in the nocturnal diuresis rate (mL/min) (that was recorded at Visit 2) as documented in the 3-day e-Diary prior to Visit 3
10. Additionally to be randomised into the trial at Visit 4 subjects must have ≥ 2 nocturnal voids (an average over 3 days) as documented in the 3-day e-Diary prior to Visit 4

^b Original inclusion criterion omitted as per Clinical Trial Protocol Amendment 02 (applicable for all trial sites).

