### 1.2 Definitions/ Abbreviations

#### 1.2.1 Definition of Terms

Terms	Definitions
Aggregated Average	Average over post-randomization visits up to and including the current visit
Baseline-ENR	Baseline measurement for the enrichment period, assessed at Visit 2
Baseline-RT	Baseline measurement for the randomized-treatment period, assessed at Visit 4
$\Delta d$	Effect of dose $d$ of FE 201836 compared to placebo
e-Diary	Electronic diary filled out by the participant at home, covering Insomnia Severity Index (ISI), Nocturia Impact Diary (NI diary), Patient Global Impression of Severity (PGI-S), Patient Global Impression of Improvement (PGI-I), HSU 5 point Likert bother scale (Bother), Voiding Diary, and IMP intake
ED85	The minimum dose most likely to have more than 85% of the effect of the maximum dose
Enrichment Period	Period between dispense of single-blind treatment and randomization
FUSP	First Undisturbed Sleep Period (FUSP) is defined as the time in minutes from the time of going to bed to the time of first nocturnal void, or time of awakening if no void occurred
MED	The minimally effective dose defined as the lowest dose that has at least a 0.3 larger reduction in mean nocturnal voids compared to placebo
$\mu d$	The mean dose-response at dose $d$ of FE 201836 corresponding to two nocturnal voids at baseline-RT
Nocturnal diuresis rate	The nocturnal diuresis rate is the ratio of Nocturnal Urine Volume (NUV, mL) to total time in bed (min)
NPi	Nocturnal Polyuria index (NPi) is calculated as the ratio of the nocturnal urine volume (NUV) by the 24-hour urine volume
NUV	Nocturnal Urine Volume (NUV) is the total urine volume from 5 minutes after bedtime with the intention to sleep until the first void within 30 minutes of rising in the morning
Pr(dose <math>d</math> is ED85)	Posterior probability that the dose $d$ is the ED 85
Pr(dose <math>d</math> is MED)	Posterior probability that the dose $d$ is the MED
Pr(<math>\Delta d < -0.3</math>)	Posterior probability that the dose $d$ has at least a 0.3 larger reduction in mean nocturnal voids compared to placebo
Pr(<math>\mu_{500} < \mu_{P1b}</math>)	Posterior probability that 500 $\mu$ g FE 201836 is superior to placebo
Safety-ENR	Safety analysis set for the enrichment period
Safety-RT	Safety analysis set for the randomized-treatment period

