## 14 Deviations From the Trial Protocol

A Full Analysis Set was defined in the protocol. However, none of the analyses specified in the trial protocol were based on the Full Analysis Set, so no Full Analysis Set has been defined in this SAP.

$Pr(\mu_d < \mu_{PLb})$  will be presented only for the 500 µg FE 201836 dose (Proof of Concept) since all doses will have the same probability because of the monotone dose-response curve parameterization; and  $Pr(\mu_d = \mu_{MAX})$  will not be displayed since it always equals 1 for the 500 µg dose, and probabilistically almost surely (that is, with probability 1) equals 0 for all other doses, again because of the monotone dose-response curve parameterization.

For some subjects, the baseline voiding diary is missing due to technical problems in the beginning of the study. The change from baseline in voiding data are considered missing completely at random for these subjects, and the subjects are not included in any analyses involving baseline measurements of voiding data.

Two sensitivity analyses have been added:

- Estimates of all quantities of interest based on the Bayesian analysis of the longitudinal model will be presented.
- A Bayesian analysis of the primary outcome with imputation using the level corresponding to placebo for drop-out.

The first sensitivity analysis presents the result for the model used for imputation. The second analysis is the Bayesian equivalent to the frequentist approach specified in the trial protocol based on a mixed model for repeated measurement (repeated-measurements ANCOVA) using MNAR placebo-based pattern mixture model.

Linear trend estimates have been added to the above mentioned protocol-specified frequentist approach as supplements to the description of the association with dose in case there are difficulties with the convergence for the primary analysis or very large uncertainties on the estimated  $\alpha$  parameters.

A secondary analysis of aggregated average change from baseline in nocturnal urine volume has been added. This outcome variable was added to comply with the Bayesian analysis mentioned in Table 9-4 in the trial protocol.

The ITT-RT data set will be used for all secondary analyses as stated in the protocol; but only observed data will be used. This is considered a clarification of the protocol.

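### The primary model adjusts only for the Visit 4 void count and leaves a comparable off-drug Visit 2 count unused, which gives up a modest amount of precision

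*SAP*

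**What the plan says.** SAP 10.2.1 models the final endpoint (the average change from baseline over Weeks 1, 4, 8 and 12) with a single baseline term, β(x0 − 2), where x0 "is the baseline-RT number of nocturnal voids". SAP 1.2.1 defines baseline-RT as "Baseline measurement for the randomized-treatment period, assessed at Visit 4". Imputation equation (3) carries the same single term. None of the seven sensitivity analyses in SAP 10.2.2 adds another void count.

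Protocol 4.1.1 requires at least 2 voids on two occasions. Criterion 5 asks for "nocturnal voids (an average over 3 days) as documented in the 3-day e-Diary prior to Visit 2". Criterion 10 asks for "nocturnal voids (an average over 3 days) as documented in the 3-day e-Diary prior to Visit 4". Everything before Visit 2 belongs to the "screening/lifestyle changes period where no IMP will be given" (Protocol 3.1.2), so the Visit 2 count is off drug. SAP Table 3 lists it as a trial assessment that is not an endpoint, and SAP 6.1.6 only summarises it as baseline-ENR. The documents give no reason for leaving it out of the model.

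**The concern.** A three-night mean measures a person's usual void count with error. When the model conditions on one such mean, part of the between-subject variation that baseline could explain stays in the residual. A second three-night mean, taken before randomisation, recovers some of it.

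Residual variance feeds the proof-of-concept rule, under which "the maximum dose has a greater than 97.5% posterior probability of being better than placebo" (Protocol synopsis). It also feeds the width of the dose contrasts and the MED and ED85 probabilities. The SAP itself allows for convergence difficulty and very large uncertainty in the curve parameters (Section 14), so precision that needs no new data is worth having.

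**Working it through.** **1. The plan's own figure.** Protocol Table 9-1 gives 90.4% power for scenario III (maximum 0.5 voids, ED50 200 µg, slope 4).
- True effect at 500 µg: 0.5 × 5⁴/(5⁴ + 2⁴) = 0.4875.
- SD 0.95, unadjusted (Protocol Appendix 2, 4.1.1); one-sided 2.5%.
- Placebo: 50 + 0.2 × 175 = 85. On 500 µg: about 82, from a simplified simulation of the adaptive allocation.
- A two-sample calculation gives 0.902 if 96% of the information survives dropout (assumed), 0.913 with full information and 0.865 with completers only.

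The 0.902 agrees with 0.904. Scenario IV does not reproduce this way (0.91 against 84.6%), so power changes are quoted for scenario III only.

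**2. Diary noise implied by the plan's longitudinal inputs** (Protocol Appendix 2, 4.1.2). Final variance is 0.95² = 0.9025 and the between-subject part is 0.90 × 0.9025 = 0.81225. Let s be the noise variance of one three-night diary. Three readings are possible:
- *Week 1 covariance.* Var(x₁) = 0.8481 × 0.9025 = 0.7654. Cov(x₁, y₄) = 0.8142 × 0.81225 = 0.6613. The average covariance of x₁ with the later changes is (4 × 0.6613 − 0.7654)/3 = 0.6266. Hence s = 0.7654 − 0.6266 = 0.139.
- *Week 1 residual.* s = 0.7654 − 0.8142² × 0.81225 = 0.227, if all of it is diary noise.
- *Final within-subject variance.* 0.10 × 0.9025 = 0.09025. If that is the mean of four independent diary errors, s = 4 × 0.09025 = 0.361.

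The readings disagree because the inputs describe running averages of change, not raw counts. They bracket s at about 0.14-0.36.

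**3. Effect of adding Visit 2.** Let B be the between-subject variance of the usual count (assumed 0.3-1.4).
- Residual given Visit 4: 0.9025 − s + Bs/(B + s)
- Residual given Visits 4 and 2: 0.9025 − s + Bs/(2B + s)

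| s | B | Visit 4 only | Visits 4 + 2 | Cut | Scenario III power |
|---|---|---|---|---|---|
| 0.139 | 0.3 | 0.859 | 0.820 | 4.5% | 0.916 → 0.927 |
| 0.139 | 0.5 | 0.872 | 0.825 | 5.5% | 0.911 → 0.926 |
| 0.139 | 1.4 | 0.890 | 0.830 | 6.8% | 0.906 → 0.924 |
| 0.227 | 1.0 | 0.861 | 0.777 | 9.7% | 0.915 → 0.939 |
| 0.361 | 0.3 | 0.705 | 0.654 | 7.3% | 0.957 → 0.969 |
| 0.361 | 1.4 | 0.829 | 0.701 | 15.3% | 0.924 → 0.958 |

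**4. Check with selection at ≥2 voids at both visits.** Simulated counts (between-subject CV 0.25-0.45, Poisson or under-dispersed nights, response SD 15-30% of baseline) gave cuts of 2.6-12.9% over 12 settings.

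**5. A model that gives more.** If all diaries are equally correlated (ρ), the residual ratio is (1 + 5ρ)/[(1 + ρ)(1 + 4ρ)]. The cut is then 7% at ρ = 0.2, 22% at 0.5 and 34% at 0.8. With both counts truncated at ≥2 it is 7-27%. But this model makes the Week 1 change variance 2(1 − ρ)/[1.25(1 − ρ)] = 1.6 times the final variance, against the plan's 0.8481, so these figures are not relied on.

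**The case against.** **No defect.** The SAP uses the covariate that the protocol pre-specified. The stated power comes from simulations fitted without baseline adjustment (Protocol Appendix 2, Adjustments in Primary Analysis), so Visit 4 already adds precision that the design does not count on. This stands: the point concerns efficiency only. The interim futility and allocation analyses are also unadjusted (SAP 12), so the change would not affect them.

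**The size is assumed.** This also stands. No correlation between the two counts is given. The selection-based simulation fits the plan imperfectly: a rebuild over 36 settings put the Week 1 variance at 1.11-1.51 times the final variance. The reading closest to the plan's Week 1 inputs points to the low end.

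**Visit 2 is not interchangeable with Visit 4.** It is about two weeks earlier, before the active run-in, and is itself a selection point. That may weaken its correlation with later counts. It does not bias randomised contrasts.

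**Stronger readings that the documents do not support:**
- *Visit 2 could rescue subjects whose baseline diary was lost.* SAP 14 says that "For some subjects, the baseline voiding diary is missing due to technical problems in the beginning of the study", but not that those subjects' Visit 2 counts survived. Protocol 4.2.1 and 7.1.1 provide for e-Diary failures before Visit 2 as well. Criterion 5 requires the count but does not prove that it can be analysed. The Visit 4 count also defines the endpoint, so imputing it is a separate and debatable step.
- *Small lower-dose groups gain most.* One common error variance shrinks in the same proportion for every group, and the contrasts come from one curve fitted across doses.
- *Reliability formulas for unselected people show larger gains.* They ignore the ≥2 selection at both visits.

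**Conclusion.** The concern holds as a missed efficiency option. A comparable, off-drug, pre-randomisation count is required by criterion 5 and is not used in the primary or imputation model. Residual variance fell in every model tried. The size rests on assumed diary noise and between-subject spread: roughly 3-15% of residual variance, usually 1-3 points of power in scenario III. If 0.95 is instead read as the SD after Visit 4 adjustment, a 15% cut would move power from 0.902 to 0.942.

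In sample-size terms, the FE 201836 and placebo groups hold about 300 − (25 + 17.5) ≈ 258 subjects. A 3% cut is worth 258 × (1/0.97 − 1) ≈ 8 more subjects, and a 15% cut 258 × (1/0.85 − 1) ≈ 45. Confidence is high on the omission and the direction, and low on where in the range the gain falls. A reader might infer that the analysis is biased or the stated power wrong; neither follows.

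**What to change.** Before unblinding, pre-specify the centred Visit 2 nocturnal-void mean as a second linear covariate, with prior N(0, 10²):
- in equation (1);
- inside the bracket of equation (3), beside the Visit 4 term;
- in the MMRM analyses of voids (SAP 10.2.2 item 7 and 10.3.4), interacting with visit as the Visit 4 baseline already does.

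State a simple rule for a missing Visit 2 count, for example the overall mean. Keep μ_d defined at 2 voids at Visit 4, and add that it also refers to the centring value of Visit 2. Leave the endpoint as change from Visit 4.

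The cost is SAP wording, a short programming change and one extra coefficient in the Bayesian model (one per visit in the MMRM). No new data are needed.
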